#### **Current standard of care for layperson at-home self-selection of PSLCs:**

In the current at-home SSE model, the layperson must first identify a specific PSL based on subjective observation. Then, the identified PSL must raise adequate concern to prompt communication with a DP through scheduling a virtual visit or requesting an in-person spot check. Currently, there is no objective prescreening method for PSLC selection or virtual visit image technical quality submission. If the layperson chooses to call and schedule an in-person visit for a new spot check appointment, the average national wait time to be seen in-person by a MD/DO dermatologist is 3 to 6 months, sometimes more. Alternatively, the layperson may choose to communicate with a DP, typically a MD/DO dermatologist, via virtual communication and send store-and-forwards SCI of their PSLC. Prior to submission, the PSLC SCI (non-medical-device assisted) image quality is not verified and often laypersons send images that are blurry, contain artifacts, or do not make it clear which PSLC is the one of concern amongst an image that contains several skin lesions (moles) in the field of view. This makes confident triage difficult for any DP in a virtual setting and often requires the DP or their team to contact the patient in order to request retaking the SCI again with better technical quality (clear image). Once an appropriate technical quality PSLC SCI is received, the DP uses non-medical-device assisted clinical judgement to make their triage decision into one of three categories:

1. **UNREMARKABLE** (no immediate concern with low clinical suspicion for malignancy, suggest the patient to self-monitor until the PSLC becomes unstable)
2. **SUSPICION** (concern with moderate to high suspicion for malignancy, recommendation to convert to an in-person visit to evaluate the PSLC with a dermatoscope, biopsy is possible)
3. **ERROR** (ask patient to retake a clear SCI image, if unsuccessful on the second attempt, convert to an in-person visit to evaluate with a dermatoscope, biopsy is possible).

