#### **Current evaluation of PSLCs by the Sklip System:**

The Sklip System may safely improve triage of layperson self-selected PSLCs in an at-home environment by transitioning a regulated triage tool (FDA Class 2) into the hands of laypersons.

After a PSLC is initially identified by the layperson, the SMSA (Sklip Ai), an artificial intelligence tool, uses objective modified dermoscopy Three-Point Checklist (MD3PC): (asymmetry (including atypical network), round structures and blue-white color) to triage PSLs into one of three categories:

1. **UNREMARKABLE** (no immediate concern, limited or no positive MD3PC, with low concern for malignancy or pre-malignancy, the SMSA output provides information and suggests the layperson to self-monitor the PSLC every three months, if the user does not understand the initial SMSA output result (Sklip Mole Scan Result) or the PSLC ever becomes unstable (changes), product labelling clearly instructs the user to contact a healthcare Provider for an in-person visit, biopsy is possible)
2. **SUSPICIOUS** (positive MD3PC with moderate to high concern for malignancy, the SMSA output result provides information and strongly suggests the layperson to contact a healthcare Provider for an in-person visit, biopsy is very possible)
3. **ERROR** (uploaded image does not meet SMSA criteria and an assessment of DDI cannot be made, the SMSA output result provides information how to properly retake DDI, if the user is unsuccessful after three (3) attempts, clear product labelling instructs the layperson to contact a healthcare Provider for an in-person visit, biopsy is possible)

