## 2.2 EXPLORATORY OBJECTIVES AND ENPOINTS

Exploratory Objectives	Endpoint	Start	End

1. To compare the accuracy of Sklip System triage when used by a layperson versus near-perfect Sklip System user
	
First, the Sensitivity of the SMSA using Study Coordinator-taken DDI (near-perfect technical quality) will be estimated to pre-specified performance goals described in sections above, using 0.05 significance level and 10% margin of error.
 
Similar to the Primary endpoint, the accuracy of SMSA output
	
First day of enrollment
	
Up to 42 days after first day of enrollment

	using Participant-taken DDI will be assessed using a 2x2 table, where the SMSA output of “SUSPICIOUS” or “UNREMARKABLE” will be compared to the SMSA output using Study Coordinator-taken DDI (near-perfect technical quality), simulating a laboratory-type environment where the SMSA is fed the best possible technical quality DDI.		
2. To assess whether Sklip System improves triage of pigmented skin lesions of concern < 6mm in diameter as suspicious as compared to the current medical provider virtual triage method that relies on store-and-forward non-medical-device assisted smartphone clinical images	Using only PSLs < 6 mm in diameter, the accuracy of the expert consensus triage decision using Participant-taken smartphone clinical images (SCI) will be assessed using a 2x2 table, where the expert consensus triage decision of “BIOPSY” or “MONITOR” will be compared to the intervention method, for both SMSA outputs recorded by Participants and SMSA outputs recorded by Study Coordinators for the same target PSLCs.	First day of enrollment	Up to 42 days after first day of enrollment
3. To assess whether Sklip System improves triage of thin melanomas with <0.8 mm Breslow depth as suspicious as compared to the current medical provider virtual triage method that relies on store-and-forward non-medical-device assisted smartphone clinical images	Using only Melanomas < 0.8 mm Breslow depth, the accuracy of the expert consensus triage decision using Participant-taken smartphone clinical images (SCI) will be assessed using a 2x2 table, where the expert consensus triage decision of “BIOPSY” or “MONITOR” will be compared to the intervention method, for both SMSA outputs recorded by Participants and SMSA outputs recorded by Study Coordinators for the same target PSLCs.	First day of enrollment	Up to 42 days after first day of enrollment

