**Description of Satellite Study required activities**

Satellite Study Sites will also complete the above activities and securely **submit** their Datasets (A-L) to the Lead Study Site via OHSU secure cloud storage services. The Lead Study Site will prepare individual Qualtrics surveys using images from the Datasets above to create the following Datasets:

Dataset M) SCI triage decision (SCI-TD) based on Datasets (D) and (I), when at least two of three expert dermatologist readers have a concordant triage decision (MONITOR or BIOPSY). If there is a lack of concordance, an internationally recognized dermoscopy expert (dermatologist) will act as a fourth reader to determine the final SCI-TD

Dataset N) DDI dermoscopic diagnosis ground truth (DDI-GT) for PSLCs that were not biopsied during the In-Person Phase, using images available in Datasets (E) and (J), when at least two of three expert dermatologist readers have a concordant dermoscopic diagnosis. If there is a lack of concordance, an internationally recognized dermoscopy expert (dermatologist) will act as a fourth reader to determine the final DDI-GT

Dataset O) Histologic diagnosis ground truth (H-GT) for lesions that were biopsied during the In-Person Phase, based on evaluations using either physical or digital histologic slides (described in Sections below), when both independent expert dermatopathologists have a concordant histologic diagnosis. If there is a lack of concordance, a third internationally recognized expert dermatopathologist will determine the final H-GT.

The Study Sponsor will be responsible for Study costs (logistics, shipping, handling, research reading fees) associated with the use of either physical or digital histologic slides to create Dataset O. If digital histologic images (DHI) are chosen, the Lead Study Site will be asked to prepare DHI for their own Study Site Participants who received a biopsy during the In-person Phase. The Lead Study Site will have the option to prepare DHI for the Satellite Study Sites.

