#### *Exploratory endpoint 2*

Using only PSLs < 6 mm in diameter, the accuracy of the expert consensus triage decision using Participant-taken smartphone clinical images (SCI) will be assessed using a 2x2 table, where the expert consensus triage decision of “BIOPSY” or “MONITOR” will be compared to the intervention method, for both SMSA outputs recorded by Participants and SMSA outputs recorded by Study Coordinators for the same target PSLCs.

The Sensitivity of the SMSA output will be compared to the Sensitivity of the expert consensus triage decision of Participant-taken SCI using McNemar’s Test, given the paired nature of the data (i.e. the same PSLCs < 6mm), using 0.05 significance level.

The Specificity of the SMSA output will be compared to the Specificity of the expert consensus triage decision of Participant-taken SCI using McNemar’s Test using 0.05 significance level.

Estimates with two-sided 95% confidence intervals will be calculated using the Exact (Clopper-Pearson) method.

This will be done for each disease entity:

- Melanoma and atypical melanocytic nevi with uncertain malignant potential,
- Squamous cell carcinoma,
- Basal cell carcinoma

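### Exploratory endpoints 2 and 3 set a device call meaning in-person review against a reader call of BIOPSY, so any difference can mix decision threshold with image type

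*Combined protocol and SAP*

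**What the plan says.** Objectives 2 and 3 (section 2.2) ask whether the device improves triage of lesions under 6 mm and of thin melanomas "as compared to the current medical provider virtual triage method that relies on store-and-forward non-medical-device assisted smartphone clinical images".

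Section 1.2 describes that comparator. Having received a photo, the provider is said to "make their triage decision into one of three categories": UNREMARKABLE, SUSPICION or ERROR. SUSPICION carries a "recommendation to convert to an in-person visit to evaluate the PSLC with a dermatoscope, biopsy is possible". For ERROR the patient retakes the photo and, "if unsuccessful on the second attempt, convert to an in-person visit to evaluate with a dermatoscope, biopsy is possible".

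The same section gives the device three parallel outputs. SUSPICIOUS "strongly suggests the layperson to contact a healthcare Provider for an in-person visit, biopsy is very possible". The output text in section 6.1.1 likewise tells the user to consult a provider in person.

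The comparator data come from Dataset M (Synopsis and section 3.1). At least two of three expert readers must reach a "concordant triage decision (MONITOR or BIOPSY" are the only two options, and a fourth reader decides if there is no concordance. Section 11.4.3 then states for endpoint 2: "The Sensitivity of the SMSA output will be compared to the Sensitivity of the expert consensus triage decision of Participant-taken SCI", by McNemar's test at the 0.05 level. Specificity is tested in the same way. Endpoint 3 has the sensitivity test only.

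**The concern.** The device's positive call and the positive call in current photo triage both mean that someone should look at the lesion in person. BIOPSY is a later and stricter action. Section 1.3 itself leaves the biopsy decision to a healthcare provider after triage.

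The missing middle option is not a rare case. Section 1.1 says that photo review tends to leave the provider unsure and often ends in conversion to an in-person visit. The survey therefore removes an outcome that the protocol regards as frequent.

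McNemar's test on these two calls cannot separate a better image and algorithm from a lower bar for a positive. The question in objectives 2 and 3 is about the first of these.

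**Working it through.** **1. The three scales side by side**

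| Scale | Negative | Positive | Not assessable |
|---|---|---|---|
| Current photo triage (1.2) | UNREMARKABLE: self-monitor | SUSPICION: in-person visit, biopsy possible | ERROR: retake, then in-person visit |
| Device (1.2, 6.1.1) | UNREMARKABLE: self-monitor | SUSPICIOUS: in-person consultation | ERROR: up to three attempts, then see a provider |
| Comparator as recorded (Dataset M) | MONITOR | BIOPSY | none |

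The first two rows match and the third does not. Nothing in the documents maps the third row onto the first or tells readers that BIOPSY includes a referral for a visit.

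**2. Adjudication.** With three readers and two options, two always agree if all three answer. The fourth-reader rule can then act only when a reading is missing. With three options a one-one-one split is possible and the rule has work to do.

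**3. Planning figures.** Formula (1) in section 11.2 gives 1.96² × 0.974 × 0.026 / (0.10² × 0.023) = 422.98, so 423 lesions. Then 423 / 1.5 × 1.10 = 310.2, so 310 participants. Both reproduce. No sample size or power is stated for endpoints 2 and 3. Expected melanomas are 423 × 0.023 = 9.7 (Table 6 shows 10), before any restriction on depth.

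**4. What a threshold shift alone could do.** This is an illustration; its assumptions are not in the documents. Assume an equal-variance binormal model in which photo reading discriminates exactly as well as the device, and move only the comparator's cut-off. With discrimination D = z(sensitivity) + z(specificity) of the device, comparator sensitivity = Φ(D − z(comparator specificity)). Table 4 supplies two starting points: 97.4% / 40% (D = 1.69) and 95% / 30% (D = 1.12).

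| Comparator specificity | Sensitivity, from 97.4/40 | Device's apparent gain (points) | Sensitivity, from 95/30 | Device's apparent gain (points) |
|---|---|---|---|---|
| 50% | 95.4% | 2.0 | 86.9% | 8.1 |
| 60% | 92.5% | 4.9 | 80.7% | 14.3 |
| 70% | 87.8% | 9.6 | 72.4% | 22.6 |
| 80% | 80.2% | 17.2 | 61.0% | 34.0 |
| 90% | 65.8% | 31.6 | 43.6% | 51.4 |

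With matched thresholds the gain is zero. The shift has a mirror image: in the first scenario the device's specificity is lower than the comparator's by 10 to 50 points (50 − 40 up to 90 − 40).

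**5. Endpoint 3 significance.** Sidedness is not stated, so take the test as two-sided. Exact McNemar with all discordant pairs in one direction gives 2 × 0.5⁵ = 0.0625 for five pairs and 2 × 0.5⁶ = 0.031 for six, so at least six are needed. With 10 melanomas and a 30-point gap due purely to threshold, P(X ≥ 6) for X ~ Binomial(10, 0.3) is 0.047. Fewer than 10 thin melanomas would make it smaller still.

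**The case against.** The strongest reply is that the direction of any bias is not documented. The survey wording and reader instructions are not given. In section 1.2 UNREMARKABLE means self-monitoring, so MONITOR corresponds to it naturally, and a reader could use BIOPSY for everything not left to monitoring. The device's SUSPICIOUS text also says that biopsy is very possible, and the primary objective concerns lesions that require biopsy, which gives a biopsy question some rationale. This stands against any claim about direction. It does not remove the undefined mapping.

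Four stronger readings are tempting, and the documents do not support them:

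- *The plan favours the device.* A stricter comparator cut-off would help the device on sensitivity and hurt it on specificity. Endpoint 2 tests both, so the trade-off would be visible there.
- *The mismatch would produce a significant result.* For endpoint 3 that is improbable (step 5). The point estimate is what would mainly be distorted.
- *Table 6 gives the number of cases at stake.* Its 10 melanomas and 21 atypical nevi cover all sizes and depths. The share under 6 mm or under 0.8 mm Breslow is not given, so there is no denominator for either endpoint.
- *Device ERROR results are simply discarded.* Under section 11.4.1 a second or third output replaces an ERROR, and only lesions with three ERRORs are excluded. That rule is written for primary and secondary endpoints. Whether it governs the exploratory ones is unstated.

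Both endpoints are exploratory, and Dataset M enters neither the ground truth nor the primary analysis.

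**Conclusion.** The concern holds as a mismatch of definitions. The comparator that will be analysed is not the comparator that objectives 2 and 3 name, because its positive call is a different and later action. Whichever way readers resolve the gap, the comparison does not cleanly answer whether the device improves on current virtual triage.

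If refer-only lesions are scored MONITOR, comparator sensitivity falls and specificity rises with no difference in image information. I think this likely, but it is an inference. Endpoint 3 has no specificity comparison to reveal it.

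The size cannot be derived from the documents. The 2 to 32 and 8 to 51 point ranges rest on the binormal model, on equal discrimination, and on assumed comparator specificities of 50% to 90%. They show only that the effect need not be negligible. The change is worth making because it is cheap, but it has no bearing on the performance-goal analysis.

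**What to change.** Before reading starts:

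1. Change the Dataset M survey (Synopsis and section 3.1) to the section 1.2 categories: UNREMARKABLE, SUSPICION with in-person evaluation, and image not assessable.
2. In sections 2.2 and 11.4.3, and the matching Synopsis text, define in-person referral as the positive call for both methods.
3. Keep BIOPSY as a second survey question for a secondary comparison.
4. State one rule for non-assessable results that covers both methods in the exploratory endpoints. One option is to exclude the pair, with a sensitivity analysis counting non-assessable as referred. Only one participant photo per lesion is collected, so the retake step cannot be reproduced.
5. Let the existing fourth-reader rule settle three-way splits.

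The readers, images, sample size and participant care stay the same. The cost is a small survey and protocol amendment, which needs committee and IRB approval under section 14.5, and more adjudication by the fourth reader. The comparator may also look better on sensitivity than under the current wording.

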## SYNOPSIS

Full Study Title	At-home dermoscopy artificial intelligence for optimizing early triage of skin cancers and atypical melanocytic nevi with uncertain malignant potential
Protocol #	STUDY00023727
Study Type	Prospective single-arm open-label multicenter research Study
Study Sample Size	310 Participants
Lead Study Site	Oregon Health and Sciences University (OHSU) in Portland, Oregon [name] (Department of Dermatology) PI: [name] [name] ( [contact] )
Satellite Study Site(s) Governance	OHSU IRB will not be responsible for governing any of the Satellite Study Sites. Their governance will be a third-party IRB using this IRB Protocol for guidance.
Study Site #2	Skin Cancer Center [name] PI: [name] MD FAAD ( [contact] )
Study Site #3	The Skin Center Dermatology Group [name] PI: [name] [name] FAAD ( [contact] )
Study Site #4	The Private Practice of [name] D.O. P.A. [name] PI: [name] DO FAOCD ( [contact] )
At-Home Phase Duration	Up to 14 days, completed by Participants at their home address
In-Person Phase Duration	Up to 28 days, completed by Participants and Study Coordinators in-office
Enrollment Duration	Up to 90 days
Abbreviated Definitions in Sequential Order	Sklip System (Sklip dermatoscope device and SMSA (used in the Sklip App)) SMSA: Sklip Mole Scanning Algorithm SCI: Smartphone clinical images (non-medical-device assisted) DDI: Digital dermoscopy images PSLC(s): Pigmented skin lesion(s) of concern FDA: United States Food and Drug Administration PMLS: Participant Mole Log Sheet SaMD: Software as a Medical Device API: Application Program Interface DP: Dermatology Provider APP: Advanced Practice Practitioner (Physicians Associate or Nurse Practitioner) PCP: Primary Care Provider MD3PC: Modified dermoscopy three-point checklist DRFs: Dermoscopic remarkable features (based on the MD3PC)

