**Schedule for data collection:**

In order to avoid Participant PSLC recollection-bias, Study Coordinators will use the Participant Mole Log Sheet (PMLS) and Participant taken SCI/DDI for guidance and **record** the following Datasets in REDCap Cloud:

- A) Total number of PSLCs identified by the Participant at-home
- B) Total number of PSLCs identified by the DP in-office
- C) One (1) individual SMSA output recorded in the PMLS, per target PSLC (SUSPICIOUS, UNREMARKABLE and ERROR)

Ensuring that no PHI is shared, Study Coordinators will **export** the following from the Participant smartphone/tablet gallery titled “Moles” to the Study Site smartphone/tablet gallery via Bluetooth or secure email:

- D) One (1) Participant-taken SCI, per target PSLC
- E) One (1) Participant-taken DDI, per target PSLC
- F) One (1) Participant-taken SMSA output screenshot, per target PSLC

Then, Study Coordinators will **acquire** and **export** the following from the Study Site smartphone/tablet gallery to an OHSU secure cloud storage service:

- G) One (1) Study Coordinator-taken DDI (near-perfect image technical quality) for each PSLC recorded in the PMLS and suspicious PSLCs identified by the DP in-office that were not recorded in the PMLS

Then, Study Coordinators will **upload** the DDI in Dataset (G) to the SMSA on a Study Site smartphone/tablet and **record** the following Datasets into REDCap Cloud:

- H) One (1) Study Coordinator-taken SMSA output for each PSLC, recorded in the PMLS, using Dataset (G) (SUSPICIOUS, UNREMARKABLE and ERROR), including one (1) screenshots

Then, the Study Coordinator will **record** the following Datasets into REDCap Cloud:

- I) All other SCI of suspicious PSLCs identified by the DP in-office that were not recorded in the PMLS
- J) All other DDI of suspicious PSLCs identified by the DP in-office that were not recorded in the PMLS
- K) Pathology reports for all PSLCs that were biopsied during the In-Person Phase
- L) Number of adverse events reported during the Study

-----End of In-person Phase-----

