### 3.2 END OF STUDY DEFINITION

A Participant is considered to have completed the Study if he/she/they have remained a Participant for the entirety of the Study period and have completed the applicable end of Study REDCap Cloud survey. Therefore, up to 14 days for the At-home Phase, including Study intervention, is sufficient time to collect data and evaluate the interventional device. Since Study Sites are required to see all Participants after the At-home Phase, up to 28 days for the In-person Phase is sufficient time to see all Participants as patients through already scheduled visits, overbookings or separate dedicated clinics. Biopsy results typically take 7 days to follow up, however Study Coordinators will continue to monitor EMR of Participants to collect relevant data up to 30 days following the end of the Study.

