#### **What should you do?**

- a) **Consult** this result in person with your established local healthcare provider, or

b) **Consult** this result in person with a dermatology provider by searching your geographic location within the Sklip network map. Click the **TAKE ACTION** button in this result to find a local dermatology office in the Sklip map.

c) **Consult** this result in person and **get a prioritized office visit within 14 days without the need for a referral**. Click the **TAKE ACTION** button in this result to find local dermatology offices in your area. Then click the **SKLIP NETWORK** filter button to identify a Sklip verified dermatology office.

*Costs associated with consulting your mole scan result with a healthcare provider are your financial responsibility and Sklip is not responsible for costs associated with medical care or verifying insurance coverage”*

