**7.6 PROHIBITED MEDICATIONS, TREATMENTS, AND PROCEDURES**

There are no restrictions on specific medications, treatments, or procedures for this study.

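### Histology from biopsies outside the In-Person Phase has no route into the ground truth, so a logged lesion proven malignant that way is scored from its image or falls out of the 2x2 table

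*Combined protocol and SAP*

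**What the plan says.** Section 3.1 sorts logged lesions by a single test, whether the biopsy fell inside the In-Person Phase.

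- Dataset O: "Histologic diagnosis ground truth (H-GT) for lesions that were biopsied during the In-Person Phase".
- Dataset N: "DDI dermoscopic diagnosis ground truth (DDI-GT) for PSLCs that were not biopsied during the In-Person Phase".
- Dataset K: "Pathology reports for all PSLCs that were biopsied during the In-Person Phase".

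The same split appears in the Synopsis, section 2.1 and section 11.4.1. The Synopsis gives the phase length: "Up to 28 days, completed by Participants and Study Coordinators in-office".

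Section 11.4.2 builds the 2x2 table on these datasets. True positives and false negatives need a biopsy diagnosis in Dataset O. True negatives and false positives use a benign ground truth from Dataset N or O. Sensitivity for squamous and basal cell carcinoma is estimated in the same manner.

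The plan also looks at charts after the phase. Section 3.1 monitors records for up to 28 days after both phases. Section 3.2 says "Study Coordinators will continue to monitor EMR of Participants to collect relevant data up to 30 days following the end of the Study". Section 8.6 has relevant pathology results recorded and analysed through chart review, and section 7.2 collects them for participants who stop using the device. Section 8.8, by contrast, says there is no scheduled follow-up and that follow-up after the 42-day Study is not the coordinators' responsibility.

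**The concern.** Histology is the better reference, and the plan sets it aside on timing alone. Biopsies outside the window are possible under the plan's own terms.

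- **Before the visit.** The SUSPICIOUS output tells the user to consult "this result in person with your established local healthcare provider", or to use a network office offering a visit within 14 days. Section 7.6 adds "There are no restrictions on specific medications, treatments, or procedures for this study".
- **After the phase.** Care follows routine pathways, so a lesion may be biopsied later. The UNREMARKABLE output advises a self-check after 1 month and then every 3 months, with a provider visit as one option if the mole changes.

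The case that matters most is a melanoma that the algorithm called UNREMARKABLE, the panel read as benign, and a later biopsy proved. The study could hold that pathology report while its primary table counts the lesion as a true negative. The primary objective is safe triage, so these are the misses that sensitivity is meant to count.

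**Working it through.** **1. Classification as written.** Take a logged lesion with malignant histology from outside the In-Person Phase.

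| SMSA output | Panel image read (Dataset N) | Cell under 11.4.2 | Cell if the histology counted |
|---|---|---|---|
| UNREMARKABLE | benign | true negative | false negative |
| SUSPICIOUS | benign | false positive | true positive |
| UNREMARKABLE | malignant | none | false negative |
| SUSPICIOUS | malignant | none | true positive |

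In all four rows the lesion leaves the sensitivity calculation.

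**2. The plan's own figures.** Formula (1) in section 11.2 gives 1.96² × 0.974 × 0.026 ÷ (0.1² × 0.023) = 422.98, so 423 lesions. Participants: 423 ÷ 1.5 × 1.10 = 310.2, so 310. Both reproduce, and neither is in question. Expected target lesions: 423 × 0.023 = 9.7 melanomas and 423 × 0.05 = 21.2 atypical nevi. These match the 10 and 21 in Table 6, a total of 31.

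**3. Effect of one lesion.** The number of misses is an assumption. The bound is the one-sided 95% Clopper-Pearson lower limit, the 0.05 quantile of Beta(x, n − x + 1).

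| True count | Estimate (lower bound) | One miss removed | Estimate (lower bound) |
|---|---|---|---|
| 30/31 | 96.8% (85.6%) | 30/30 | 100% (90.5%) |
| 29/31 | 93.5% (81.1%) | 29/30 | 96.7% (85.1%) |
| 28/31 | 90.3% (76.8%) | 28/30 | 93.3% (80.5%) |

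Table 6's own split has 9 + 14 = 23 of the 31 flagged suspicious: 23/31 = 74.2%, becoming 23/30 = 76.7%. The shift is about 3 points in each case. Only 29/31 crosses 95%, and only on the point estimate. Even 31/31 has a lower bound of 0.05^(1/31) = 90.8%.

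**4. The opposite direction.** A SUSPICIOUS lesion removed elsewhere before the visit costs a true positive: 29/31 = 93.5% becomes 28/30 = 93.3%. Per lesion, this is much smaller than losing a miss.

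**5. Specificity.** With Table 6's 107 non-suspicious of 220 negative lesions, one miss counted as a true negative moves 107/220 = 48.6% to 108/221 = 48.9%, which is negligible.

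**6. Timing.** At-home scans fall within days 1 to 14 and the phases end by day 14 + 28 = 42. Taking a month as 30 days, the first self-check falls on about days 31 to 44, near the end of the phase. Chart monitoring ends on about day 70 (42 + 28) or day 72 (42 + 30). The next self-check, 90 days after the first, falls on about days 121 to 134, beyond either limit.

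**The case against.** The strongest reply is that the plan already collects these data. Section 3.1 monitors charts to pick up what was not collected during the Study, and section 8.6 says relevant pathology is recorded and analysed. On that view only a linking sentence is missing. Much of this stands: collection is planned and the repair is small. But general wording on collection does not override explicit dataset and cell definitions, and nothing in the documents moves such histology into Dataset K or O.

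A second reply is that the event is rare. A biopsy on a later day within the 28-day phase still counts as histology. Participants are directed to the study site, and sites agree to overbook. A late-proven miss also requires the algorithm to miss the lesion, the blinded provider to leave it unbiopsied and the panel to read it as benign, all before a biopsy within about 30 days. This stands as an argument about frequency. The documents give no rate.

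A reader might go further and infer that out-of-window biopsies are expected, that the rule always inflates sensitivity, or that one lesion would turn failure into success. The documents support none of these. The output labels and section 7.6 make outside biopsies possible, not expected. Early outside biopsies of SUSPICIOUS lesions lower sensitivity. No rule makes the point estimate decisive; section 11.4.2 specifies a one-sided lower bound, and no result on 31 lesions brings that bound to 95%.

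That the ground-truth method was discussed with the FDA does not settle the matter either, because nothing says out-of-phase histology was considered.

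**Conclusion.** The gap is real, and confidence in the reading of the text is high: malignant histology from outside the In-Person Phase cannot make a lesion a true positive or false negative. The effect is less certain. It rests on an unknown and probably low number of such biopsies, and its net direction is not fixed. On about 31 expected lesions, one late-proven miss raises the point estimate by about 3 points, while one lost true positive lowers it by a few tenths at most when sensitivity is in the 90s. These counts are illustrative.

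I rate this as moderate. It concerns the reference standard of the primary endpoint and is cheap to correct, but a reader should not infer that it invalidates the trial or would by itself decide the outcome. The wider question of using an image reference for lesions never biopsied is separate and is not resolved here.

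**What to change.** Amend the definitions before outcomes are known, so that no proven cancer has to be reclassified after the fact.

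- Define Datasets K and O as any histology of a logged lesion, from the at-home scan to one stated data cut-off at the end of the existing chart-monitoring period. Use the local pathology report where slides cannot be obtained for expert review.
- Restrict Dataset N to logged lesions with no histology by that cut-off.
- Reconcile the 28 days in section 3.1, the 30 days in section 3.2 and the disclaimer in section 8.8, so that the cut-off is unambiguous.
- Carry the new definitions into the Synopsis and sections 2.1, 11.4.1 and 11.4.2, and report the in-phase-only definition as a sensitivity analysis.

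The sample size (423 lesions, 310 participants) and clinical care do not change. The cost is amended wording and a small number of slide or report requests. Ground truth locks slightly later, and some outside slides may be unobtainable. Misses proven after the cut-off remain uncounted, which the report should state.
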